9.2 SAMPLE SIZE DETERMINATION

Based on the primary variable of the intervention, the percentage of T2DM remission, the required sample size has been calculated to observe statistically significant differences. This variable will be coded dichotomously. A total of 120 volunteers (60 per arm) will be recruited for the study. Accepting an alpha risk of 0.05 (5%) and a beta risk of less than 0.2 in a two-sided test, at least 52 subjects in the control group and 52 subjects in the intervention group would be required to detect as statistically significant a 20% difference between two proportions (primary endpoint: T2DM remission). For the control group, the expected remission rate ranges from 0 to 5%, whereas in the intervention group, it is expected to be at least 25%. The remission rates have been benchmarked against previous studies (Lean et al., n.d.). An estimated loss to follow-up rate of 15% has been considered.

Given the estimated 15% loss to follow-up, the sample size has been increased to 60 participants instead of 52. This ensures that the statistical power of the analysis will be preserved.

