9.4.3 ANALYSIS OF THE SECONDARY ENDPOINT(S)

The secondary endpoint is diabetes remission at 18 months, defined as achieving HbA1c <6.5% without glucose-lowering medications. It will be analyzed using a generalized linear mixed-effects model (GLMM) with a logit link, including treatment group, time, and group \times time interaction as fixed effects, and a random intercept for participants to account for repeated measurements. Prespecified covariates include baseline HbA1c, age, sex, site, and randomization block. Results will be reported as adjusted odds ratios with 95% confidence intervals and two-sided p-values.

The analysis will follow the Intention-to-Treat (ITT) principle; a Per-Protocol (PP) analysis (adherence $\geq 70\%$) will be performed as sensitivity. Missing data will be handled under the missing-at-random assumption, with multiple imputation applied if necessary. Trajectories of remission probabilities over time will also be presented.

Others secondary endpoints include:

- Change in body weight (kg) from baseline to 6 months (continuous, interval scale).
- Change in blood pressure (systolic and diastolic, mmHg) from baseline to 6 months (continuous, interval scale).
- Change in lipid profile (total cholesterol, LDL-C, HDL-C, triglycerides, mg/dL) from baseline to 6 months (continuous, interval scale).
- Change in circadian rhythm regularity (measured via validated questionnaire scores; ordinal/interval scale).

- Change in health-related quality of life (measured via validated scale, e.g., SF-12 or equivalent; interval scale).
- Intervention adherence (measured as percentage of scheduled sessions completed; continuous, but categorized as adherent $\geq 70\%$ vs. non-adherent for analysis).

The analysis models for continuous outcomes (e.g., weight, blood pressure, lipid levels, quality of life scores) will be analyzed using ANCOVA with treatment group as a fixed factor and baseline values as covariates. Repeated measures across timepoints (baseline, 3 months, 6 months) will be analyzed with MMRM to account for within-participant correlations.

For binary/categorical outcomes (e.g., adherence $\geq 70\%$, achievement of HbA1c $< 6.5\%$) will be analyzed using logistic regression, adjusted for prespecified covariates.

For ordinal outcomes (e.g., circadian rhythm scores if treated as ordinal), ordinal logistic regression will be considered.

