All analyses will adjust for baseline values of each outcome, plus prespecified covariates such as age, sex, and site. Covariate selection will be guided by clinical relevance and baseline comparability, aiming for a parsimonious model.

Results will be reported as adjusted mean changes with standard errors (for continuous outcomes), odds ratios with 95% confidence intervals (for binary/ordinal outcomes), and associated p-values. For binary endpoints, absolute risk differences and numbers-needed-to-treat (NNT) will also be reported when applicable.

The same approach as for the primary endpoint will be applied: MMRM for repeated measures (implicitly handling missing values under MAR) and multiple imputation for single-timepoint ANCOVA analyses. Sensitivity analyses will evaluate the robustness of results.

Normality and homoscedasticity will be checked for continuous outcomes. Logistic regression models will be checked for linearity in the logit and absence of multicollinearity. Ordinal models will be checked for proportional odds assumption.

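### Remission is to be reported as an adjusted odds ratio although only 0 to 5% of controls are expected to remit, so the estimate may be infinite or very imprecise

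*Protocol*

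**What the plan says.** Section 9.4.3 makes diabetes remission at 18 months the leading secondary endpoint. The model is a logit mixed model with group, time, their interaction and a random intercept, adjusted for baseline HbA1c, age, sex, site and randomization block. On the output it says: "Results will be reported as adjusted odds ratios with 95% confidence intervals and two-sided p-values". Other binary outcomes, among them reaching HbA1c below 6.5%, get adjusted logistic regression, again summarised by odds ratios. The section adds that for binary endpoints "absolute risk differences and numbers-needed-to-treat (NNT) will also be reported when applicable". The checks named for logistic models are linearity in the logit and multicollinearity.

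Section 9.4.1, in its paragraph on the primary efficacy analysis, also plans absolute risk reduction, relative risk reduction and number needed to treat, without the applicability condition.

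Section 9.2 gives the expected rates for the primary variable, remission at 6 months: "For the control group, the expected remission rate ranges from 0 to 5" per cent, and for the intervention arm "it is expected to be at least 25" per cent. On numbers it says "at least 52 subjects in the control group and 52 subjects in the intervention group would be required" and "A total of 120 volunteers (60 per arm) will be recruited for the study". The trial is sized on a 20-point difference between two proportions.

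**The concern.** An odds ratio needs events in both arms. The protocol's own planning range for controls runs from none to about three, and its lower end is exactly zero. If no control remits, the group effect is perfectly separated: the likelihood keeps rising as the log odds ratio grows, so there is no finite estimate. Software then usually prints a huge coefficient with a huge standard error, and the Wald p-value is close to 1 even when the arms clearly differ. A random intercept does not remove separation in a fixed effect.

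A second source is possible. Section 8.1 records presence of remission at baseline as well as at follow-up, and entry requires HbA1c above 6.5% (Section 5.1), so baseline remission is about zero in both arms. If baseline enters the mixed model as a repeated time point, the time and interaction terms separate too.

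At stake is whether the effect measure named for the leading secondary endpoint can be reported with a usable interval and p-value.

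**Working it through.** **Inputs.** Control rate 0 to 5%, intervention rate at least 25%, 52 per arm required, 60 per arm recruited, 15% loss (all Section 9.2). With that loss, 60 × 0.85 = 51 evaluable per arm. The UK primary-care weight-management trial described in Section 2.2 had 4% remission in its control group.

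**The plan's own figure.** For 5% against 25% ("Accepting an alpha risk of 0.05 (5%) and a beta risk of less than 0.2 in a two-sided test"), the pooled formula gives 49 per arm, the continuity-corrected formula 59, and the arcsine formula 44.2. The last, divided by 0.85, is 52.0 and matches the stated 52. Power with 52 per arm is 82.5%. The size is not at issue here. It shows that 5% against 25% on the proportion scale is the design contrast.

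**Expected control events.** 52 × 0.05 = 2.6 and 60 × 0.05 = 3.0 at the upper end, 0 at the lower end. Intervention: 52 × 0.25 = 13.

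**Chance of no control remission**, (1 − p)^n:

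| True control rate | n = 51 | n = 52 | n = 60 |
|---|---|---|---|
| 5% | 7% | 7% | 5% |
| 4% | 12% | 12% | 9% |
| 3% | 21% | 21% | 16% |
| 2% | 36% | 35% | 30% |
| 1% | 60% | 59% | 55% |
| 0% | 100% | 100% | 100% |

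**With no control event: 0/52 against 13/52.**
- The ordinary logistic fit diverges: log odds ratio about 23, standard error about 18,000, Wald p about 0.999.
- The likelihood-ratio statistic is 2 × [13 ln 0.25 + 39 ln 0.75 − (13 ln 0.125 + 91 ln 0.875)] = 2 × (−29.24 + 39.18) = 19.9 on 1 df, p about 0.00001. Fisher's exact p is 0.0001.
- Adding one half to each cell, which is the Firth estimate in a 2 × 2 table, gives (13.5 × 52.5)/(0.5 × 39.5) = 35.9, with a Wald-type 95% interval of 2.1 to 622.
- For the near-identical 0/51 against 13/51, the Miettinen-Nurminen risk difference is 25.5% (95% CI 15.5 to 38.9).

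**With 1, 2 or 3 control events against 13/52**, the unadjusted odds ratios are:
- 1 event: (13 × 51)/(1 × 39) = 17.0 (95% CI 2.1 to 136)
- 2 events: (13 × 50)/(2 × 39) = 8.3 (1.8 to 39)
- 3 events: (13 × 49)/(3 × 39) = 5.4 (1.5 to 20)

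That is 14 to 16 events in total, before five covariates are added.

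**If baseline is a time point.** A fixed-effects logit fit used 52 per arm, no baseline remissions, 2 control remissions at each follow-up, and 13 then 11 in the intervention arm. Standard errors are about 18,000 to 26,000 on the group, time and interaction terms. The 18-month contrast can still be recovered as the group term plus the interaction (0 + 1.90, that is ln[(11 × 50)/(2 × 41)]). The protocol does not say which contrast is reported.

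All fits here are fixed-effects and without covariates.

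**The case against.** Several points on the other side stand.

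- A logit model with odds ratios is a normal choice for a binary endpoint, and a statistical analysis plan that is not shown may name a fallback for separation. So the absence of one is not the point made here. The point is that the stated effect measure fits badly with the stated rates.
- The 0 to 5% range belongs to remission at 6 months. Using it at 18 months is an assumption. It is a reasonable one, because the 18-month definition asks for at least 9 months off medication rather than 3. The range does not carry over to reaching HbA1c below 6.5%, which as worded has no medication-free condition and may be commoner in controls.
- At the rates that anchor the design, 4 to 5%, the chance of no control event is only 5 to 12%. The chances of 30% or more need a true rate of 2% or less.
- The protocol does not specify Wald inference. A likelihood-ratio test within the same logistic framework keeps its meaning, so only the point estimate and Wald-based results fail.
- Baseline HbA1c is a covariate and Section 9.4.3 lists no time points for the remission model, so baseline may not be an outcome time at all.

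Two stronger readings are tempting and are not supported. One is that risk differences appear only conditionally: Section 9.4.1 plans absolute risk reduction and number needed to treat without that condition. The other is that the model fails just when the intervention succeeds: the chance of zero control events depends on the control rate alone.

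**Conclusion.** The concern holds as one of robustness. On the protocol's own range, the planned odds ratio for remission is either infinite, with a chance of about 5 to 12% at control rates of 4 to 5% and 30 to 36% at 2%, or finite with a 95% interval whose upper limit is 13 to 64 times its lower limit (20/1.5 and 136/2.1). This rests on a control rate at 18 months similar to or lower than the one given for 6 months, and on 51 to 60 evaluable controls. The baseline problem is conditional on baseline being modelled as an outcome time.

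A reader might infer that the trial could not demonstrate an effect on remission. It could: likelihood-ratio and exact tests, and the risk difference, all give clear answers on the same counts. What is weak is the choice of lead measure. The absolute measures already planned are additions, no interval method is named for them, and they are on the scale on which the trial was sized. The change should be made before the data are seen.

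**What to change.** In Section 9.4.3, and wherever remission is reported:

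1. Make the difference in remission proportions at 6 and at 18 months the main reported effect. Give a score-type 95% interval such as Miettinen-Nurminen, stratified or standardised over the stratification factors. The four two-level factors make 2 × 2 × 2 × 2 = 16 strata, or 104/16 = 6.5 evaluable participants each on average, so choose weights that tolerate sparse strata.
2. Report the odds ratio as supportive, from Firth-penalised logistic regression with a profile-likelihood interval and test.
3. Restrict the repeated remission model to post-baseline times, and name the contrast to be reported.
4. Remove the applicability condition on the risk difference for remission.

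The cost is wording and a little programming, with no new data, visits or participants. The drawback is that results will be less directly comparable with published odds ratios, such as the 19.7 quoted in Section 2.2. The supportive odds ratio covers part of that loss.

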3 OBJECTIVES AND ENDPOINTS

OBJECTIVES	ENDPOINTS	JUSTIFICATION FOR ENDPOINTS

Primary
 
To quantify the percentage of type 2 diabetes (T2DM) reversal among participants without signs of absolute insulinopenia enrolled in the CREDOenAP lifestyle intervention program at the end of the program (6 months).
	
Percentage of participants achieving type 2 diabetes (T2DM) remission at 6 months, defined as HbA1c <6.5% after 6 months of intervention and at least 3 months without antidiabetic medication. HbA1c will be measured from fasting venous blood samples (minimum 8 hours fasting).
 
Percentage of participants achieving T2DM remission at 6 months, defined as fasting venous plasma glucose <126 mg/dL after 6 months of intervention and at least 3 months without antidiabetic medication. Fasting plasma glucose will be measured from venous blood samples after a minimum 8-hour fast.
	
These measures allow evaluation of the intervention's efficacy, as they are widely accepted indicators of type 2 diabetes (T2DM) remission. These criteria have been consensually established and accepted by international organizations such as the American Diabetes Association (ADA) and the European Association for the Study of Diabetes (EASD).

Secondary		
1. To quantify the percentage of type 2 diabetes (T2DM) remission among participants in the CREDOenAP lifestyle intervention program one year after completing the program (18 months).	
Percentage of participants maintaining type 2 diabetes (T2DM) remission at 18 months, defined as HbA1c <6.5% after 12 months following the intervention and at least 9 months without antidiabetic medication.
 
Percentage of participants maintaining T2DM remission at 18 months, defined as fasting venous plasma glucose <126 mg/dL after 12 months following the intervention and at least 9 months without antidiabetic medication
	
These measures allow evaluation of the efficacy and long-term sustainability of the intervention, as they are widely accepted indicators of type 2 diabetes (T2DM) remission. These criteria have been consensually established and accepted by international organizations such as the American Diabetes Association (ADA) and the European Association for the Study of Diabetes (EASD).

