2. To assess dietary patterns, physical activity, and health-related quality of life of participants in the CREDOenAP program at the end of the intervention and one year later.	
Change in dietary patterns at 6 and 18 months, assessed using a validated 24-hour recall questionnaire, to evaluate adherence to the nutritional component of the intervention.
 
Change in physical activity levels at 6 and 18 months, measured using the International Physical Activity Questionnaire (IPAQ).
 
Change in health-related quality of life at 6 and 18 months, assessed using validated instruments such as the SF-36 or EQ-5D questionnaires.
	
Changes in the scores of the aforementioned questionnaires will allow evaluation of changes in dietary patterns, physical activity, and health-related quality of life.

3. To assess anthropometric, metabolic, and imaging markers for cardiovascular risk evaluation in participants of the CREDOenAP	Change in cardiovascular risk factors at 6 and 18 months, including blood pressure, total cholesterol, HDL cholesterol, LDL cholesterol, Apo B100, triglycerides, and the presence and	These measures will allow evaluation of key underlying mechanisms contributing to type 2 diabetes (T2DM) remission.

program at the end of the intervention (6 months) and one year later (18 months).	size of carotid atherosclerotic plaques. Change in metabolic indicators at 6 and 18 months, assessed through weight, body mass index (BMI), waist circumference, insulin resistance (HOMA-IR), pancreatic beta-cell function (HOMA-B), and fasting insulin levels.	
Tertiary/Exploratory		

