9 STATISTICAL CONSIDERATIONS

9.1 STATISTICAL HYPOTHESES

Primary Endpoint:

The primary hypothesis is based on the null hypothesis (H_0), which states that there is no difference in the percentage of type 2 diabetes (T2DM) remission between the intervention group and the control group. Conversely, the alternative hypothesis (H_1) states that the percentage of T2DM remission will be significantly higher in the intervention group compared to the control group. An efficacy analysis is planned and will be evaluated right after the end of the intervention.

Secondary Endpoints:

The null hypothesis (H_0) states that there will be no significant differences in the proposed secondary variables (metabolic, behavioral, and quality-of-life variables) between the intervention group and the control group. Conversely, the alternative hypothesis (H_1) states that there will be statistically significant differences in the proposed secondary variables (metabolic, behavioral, and quality-of-life variables), with more favorable outcomes for the intervention group compared to the control group. An efficacy analysis of the intervention is planned, and the evaluation will be carried out 12 months after the end of the intervention.

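### Section 9.4.3 does not match the secondary endpoints of Section 3: weight, blood pressure and lipids stop at 6 months, ten endpoints go unnamed, and instruments and outcomes differ

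*Protocol*

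**What the plan says.** **Section 3 (and the synopsis).** Remission at 18 months is defined twice, by HbA1c and by glucose: "Percentage of participants maintaining T2DM remission at 18 months, defined as fasting venous plasma glucose <126 mg/dL after 12 months following the intervention". The remaining secondary endpoints carry two time points, for example "Change in metabolic indicators at 6 and 18 months, assessed through weight, body mass index (BMI), waist circumference, insulin resistance (HOMA-IR", "Change in dietary patterns at 6 and 18 months, assessed using a validated 24-hour recall questionnaire" and "Change in physical activity levels at 6 and 18 months, measured using the International Physical Activity Questionnaire (IPAQ". Blood pressure, lipids, Apo B100 and carotid plaque are also set at 6 and 18 months. Quality of life is by SF-36 or EQ-5D. Circadian habits are exploratory, with a custom questionnaire.

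**Section 8.1.** All secondary outcome variables are measured at baseline, at the end of the programme and a year later. Circadian habits appear in this secondary group, by a study-specific questionnaire. Quality of life is the SF-36.

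**Section 9.1.** The alternative hypothesis is that "there will be statistically significant differences in the proposed secondary variables", and "the evaluation will be carried out 12 months after the end of the intervention".

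**Section 9.4.3.** HbA1c-defined remission at 18 months is singled out as the secondary endpoint. The others listed are weight ("Change in body weight (kg) from baseline to 6 months (continuous, interval scale"), blood pressure and four lipids, all to 6 months, followed by circadian regularity, quality of life and session adherence with no time point. The repeated-measures model uses baseline, 3 and 6 months. "Results will be reported as adjusted mean changes with standard errors (for continuous outcomes"), with p-values.

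**The concern.** The analysis section should operate on the endpoints that the objectives section defines. Here the two differ in membership, in timing and in instrument. An analyst who follows 9.4.3 would produce no 18-month comparison of weight, blood pressure or lipids, which is half of what secondary objective 3 asks. An analyst who follows Section 3 would produce a different set of results. Both could claim to have followed the protocol, so the choice of list and time point stays open until the data are seen. The choice matters more because 9.1 states the secondary hypothesis as significance across the set, and 9.4.1 puts every test at two-sided 0.05.

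**Working it through.** **1. Membership.** Blood pressure is counted as one item and carotid plaque as one.

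- Section 3, 18 items: remission at 18 months by HbA1c; remission at 18 months by glucose; diet; IPAQ; quality of life; blood pressure; total cholesterol; HDL; LDL; Apo B100; triglycerides; carotid plaque; weight; BMI; waist; HOMA-IR; HOMA-B; fasting insulin.
- Section 9.4.3, 10 items: remission at 18 months by HbA1c; weight; blood pressure; total cholesterol; LDL; HDL; triglycerides; circadian regularity; quality of life; adherence.
- In both: 8. Only in Section 3: 18 − 8 = 10 (glucose-defined remission, diet, IPAQ, Apo B100, carotid plaque, BMI, waist, HOMA-IR, HOMA-B, fasting insulin). Only in 9.4.3: 10 − 8 = 2 (circadian regularity, adherence).

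**2. Timing.**

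| Item | Section 3 | Section 9.1 | Section 9.4.3 |
|---|---|---|---|
| HbA1c-defined remission | 18 months | 18 months | 18 months |
| Weight, blood pressure, lipids | 6 and 18 months | 18 months (6 + 12) | 6 months |
| Repeated-measures model | – | – | 0, 3, 6 months |
| Quality of life | 6 and 18 months | 18 months | not stated |

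The remission row agrees throughout. The second row does not. The 18-month data will exist: Section 1.3 schedules laboratory tests, anthropometry, carotid ultrasound and questionnaires at that visit, and 8.1 says the same of all secondary variables.

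**3. Adherence.** It is the share of scheduled sessions completed, cut at 70% and assigned to logistic regression among the secondary endpoints. Section 4.1 gives controls no part of the programme, so they have no sessions to complete. The quantity is undefined or zero by construction in that arm, and no between-arm contrast exists.

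**4. Instruments.**

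| Construct | Section 3 | Section 8.1 | Section 9.4.3 |
|---|---|---|---|
| Quality of life | SF-36 or EQ-5D | SF-36 | SF-12 or equivalent |
| Circadian habits | exploratory, custom | secondary, study-specific | secondary, called validated |

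The schedules in 1.3 and 8.1 name only the SF-36.

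**5. Scale of the unranked hypothesis.** The chance of at least one false positive in k independent true-null tests is 1 − (1 − 0.05)^k. For k = 18, one test per Section 3 item, this is 1 − 0.95^18 = 0.60. The outcomes are correlated (weight with BMI and waist; insulin with HOMA-IR and HOMA-B), so the actual figure would be lower.

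**The case against.** Several points on the other side stand.

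- *The ten items are not necessarily dropped.* 9.4.3 introduces its list with the word *include*, and its model rules for continuous and binary outcomes are generic enough to cover most of the ten. A reader might infer that these endpoints will go unanalysed. The protocol does not say so, and 8.1 has them measured. An open-ended list does not, however, explain the 6-month limit on endpoints that it does name, nor the adherence item.
- *Section 9.1 may only say when the evaluation is done*, once 18-month data are in, and need not exclude 6 months. The firm conflict is between Section 3 and 9.4.3; 9.1 needs clarifying.
- *Circadian regularity is not an arbitrary insertion.* 9.4.3 follows 8.1 here. The disagreement is with Section 3, and over the word validated.
- *Multiplicity rules are commonly left to an SAP*, which is not shown, so their absence is no fault. 9.1 also words its hypothesis collectively. A reader might count finely (eight SF-36 domains, split blood pressure and plaque, both times), reach 25 × 2 + 2 = 52 tests and compute 1 − 0.95^52 = 0.93. The documents fix no such count: the instrument is left open, 9.4.3 itself drops 18 months for several items, and independence does not hold. That figure should not be used.
- *There is some order already.* 9.4.3 sets HbA1c-defined remission at 18 months apart from the others. Formal gating on the primary is not proposed, because Section 3 gives two remission definitions as primary while 9.4.2 names HbA1c change, so there is no single gate.
- *The ANCOVA yields a between-arm contrast anyway.* True; the reporting sentence is loosely worded, and the missing confidence interval for continuous outcomes is the fair part of that complaint.

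**Conclusion.** The contradiction is real and worth correcting before any outcome data are seen. Its core is timing: the 18-month part of secondary objective 3 has neither an endpoint definition nor a model in 9.4.3 for the very variables that 9.4.3 lists. Around it are ten endpoints not named out of 18, one added outcome with no between-arm meaning, and two constructs with conflicting status or instrument. The count of ten rests on treating plaque presence and size as one item; it is eleven if they are split.

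The 18-month HbA1c-defined remission endpoint is not affected by the timing conflict. The 60% figure illustrates scale under independence with one test per item; it does not estimate this trial's error rate. The documents do not support saying that the ten endpoints have been abandoned, or that the protocol fails for want of a multiplicity adjustment.

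**What to change.** - Use one secondary endpoint list, identical in Sections 3, 8.1 and 9.4.3, with every non-remission endpoint at both 6 and 18 months.
- Add 18 months to the repeated-measures model in 9.4.3.
- State in 9.1 that the secondary endpoints are evaluated at both times.
- Name the SF-36 as the quality-of-life instrument throughout, since it is the one scheduled.
- Give circadian habits a single status and call the questionnaire study-specific.
- Report adherence descriptively, in the intervention arm only.
- Report continuous secondaries as adjusted between-arm differences with 95% CIs.
- Keep HbA1c-defined remission at 18 months as the lead secondary, label the others supportive, and reword the hypothesis in 9.1 to match.

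The cost is protocol wording. No visit, test or participant is added, because the Section 3 outcomes are already planned at both times. The sponsor gives up claims of significance on the supportive secondaries.
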